#### **Database Lock and Study Unblinding**

Once the database has been locked, randomized treatment assignments will be obtained from the IXRS vendor after obtaining proper authorization from Aimmune. These treatment assignments will then be incorporated into the analysis datasets, tables, listings, and figures.

#### 2.6. ADMINISTRATION OF STUDY TREATMENT

The Initial Escalation period, Day 1, dosing schedule and Up-dosing period dosing schedule are shown in the following two tables:

#### Table 2.2 Initial Escalation Period, Day-1, Dosing Schedule

	Initial Escalation Period, Day 1, Dosing Schedule		
Day 1 Dose #	Study Product Dose (mg peanut protein or placebo)	Cumulative Study Product Dose (mg peanut protein or placebo)	
1	0.5	0.5	
2	1	1.5	
3	1.5	3	
4	3	6	
5	6	12	

Doses will be delivered at 20 to 30 minute intervals.

Subjects who are unable to tolerate a dose of 3 mg at the end of Day 1 will be considered escalation failures.

All subjects who tolerate a dose of at least 3 mg on Day 1 will return on Day 2 to receive a single confirmatory 3 mg dose under direct observation.

Subjects with either no symptoms or mild, non-dose-limiting symptoms after receiving 3 mg on Day 2 may start 2 weeks of daily dosing at 3 mg.

Subjects who experience moderate or severe symptoms after receiving the 3 mg dose on Day 2 will be considered escalation failures.

Future dose escalations will occur every 2 weeks with the initial dose increase administered in the clinical research center.

Up-dosing Period Dosing Schedule			
Up-dosing Dose #	Study Product Dose (mg peanut protein or placebo)	Interval (weeks)	% Increase
1	3	2	
2	6	2	100%
3	12	2	100%
4	20	2	67%
5	40	2	100%
6	80	2	100%
7	120	2	50%
8	160	2	33%
9	200	2	25%
10	240	2	20%
11	300	Enter Maintenance Period	25%

#### Table 2.3 Up-dosing Period Dosing Schedule

Capsules and sachets (introduced during the Maintenance Period) are opened, contents sprinkled over an age-appropriate food, and mixed thoroughly. 300 mg capsules will be used for at least the first 2 weeks of dosing during the 24-Week Maintenance Period.

All subjects who reach and tolerate 300 mg/d will continue at that dose level for the

duration of the Maintenance Period. The first Maintenance visit occurs 2 weeks after the last Up-Dosing visit, with visits every 4 weeks thereafter. For the Maintenance Period, 300 mg of peanut protein will be formulated in foil-laminate sachets. Matching placebo sachets will be used to maintain the double-blind. Any subject unable to achieve a dose of 300 mg/d of peanut protein by 40 weeks will be considered an escalation failure non-responder and will not undergo Exit DBPCFC.

#### 2.7. DOUBLE BLIND PLACEBO CONTROLLED FOOD CHALLENGE

The DBPCFC at screening and exit will consist of administering gradually increasing challenge doses of peanut flour (containing ~50% peanut protein) or placebo (oat flour), mixed in a vehicle food, at 20 to 30 min intervals. The DBPCFC will be performed in accordance with Practical Issues in Allergology, Joint United States/European Union Initiative (PRACTALL) guidelines, but requiring progression in an unaltered sequence without repeating any dose. The DBPCFC is to be conducted as 2 challenges, each on a separate day, using a placebo for one challenge and peanut for the other, with similar artificial flavorings added to each as masking agents. The 2 challenge days should be scheduled as closely together as practicable and should not be scheduled more than 7 days apart. The oral food challenge is to be performed under double-blind conditions so that neither the subject, nor the subject's caregiver, nor any of the clinic staff (save for the unblinded preparer of the challenge foods) knows which challenge contains the peanut or the placebo. The clinic staff may not be unblinded as to the order of the two parts (peanut and placebo) of the DBPCFC until after completion of the observation period of the second part of the challenge.

For each subject, a "blinded" Evaluating Physician (Blinded Assessor) is to be designated to assess the tolerability of the challenge doses presented in the DBPCFC. The Blinded Evaluating Physician is not to be involved in the oversight of study product dosing (neither Initial Escalation, nor Up-dosing), nor the assessment or management of adverse events. To the extent practicable, the same Blinded Evaluating Physician who determines DLSs in the Screening DBPCFC should determine DLSs in the Exit DBPCFC.

The Screening and Exit DBPCFCs are based on a modified PRACTALL dosing regimen as illustrated in Table 2.4.

# Table 2.4.Modified PRACTALL DBPCFC Doses Using Peanut Flour with 50%
Peanut Protein Content for Screening and Exit DBPCFC

	Challenge Doses			
	Amount of Peanut Protein at Each Challenge Dose (mg)	Amount of Peanut Flour with 50% Protein Content (mg)	Cumulative Amount of Peanut Protein (mg) at Screening	Cumulative Amount of Peanut Protein (mg) at Exit
Screening only	1	2	1	0 (or 1)*
Screening and Exit	3	6	4	3 (or 4)
Screening and Exit	10	20	14	13 (or 14)
Screening and Exit	30	60	44	43 (or 44)
Screening and Exit	100	200	144	143 (or 144)
Exit only	300	600	-	443 (or 444)
Exit only	600	1200	-	1043 (or 1044)
Exit only	1000	2000	-	2043 (or 2044)

\*For explanation of contingent/optional doses indicated in parentheses refer to protocol Section 6.6.2

#### **3. ENDPOINTS**

### **3.1. PRIMARY EFFICACY ENDPOINT**

For North America, the primary efficacy endpoint is the proportion of subjects ages 4-17 who tolerate a single highest dose of at least 600 mg (1043 mg cumulative) of peanut protein with no more than mild symptoms at the Exit DBPCFC.

For Europe, the primary efficacy endpoint is the proportion of subjects ages 4-17 who tolerate a single highest dose of at least 1000 mg (2043 mg cumulative) of peanut protein with no more than mild symptoms at the Exit DBPCFC.

#### **3.2. SECONDARY ENDPOINTS**

#### 3.2.1. Key Secondary Efficacy Endpoints

North America: The hierarchal order of key secondary efficacy endpoints is as follows:

- 1. The proportion of subjects ages 4-17 who tolerate a single highest dose of at least 300 mg (443 mg cumulative) of peanut protein with no more than mild symptoms at the Exit DBPCFC
- 2. The proportion of subjects ages 4-17 who tolerate a single highest dose of at least 1000 mg (2043 mg cumulative) of peanut protein with no more than mild symptoms at the Exit DBPCFC
- 3. The maximum severity of symptoms in subjects ages 4-17 occurring at any challenge dose of peanut protein during the Exit DBPCFC
- 4. The proportion of subjects aged 18 to 55 years who tolerate a single highest dose of at least 600 mg (1043 mg cumulative) of peanut protein with no more than mild symptoms at the Exit DBPCFC

Europe: The hierarchal order of key secondary efficacy endpoints is as follows:

- 1. The proportion of subjects ages 4-17 who tolerate a single highest dose of at least 600 mg (1043 mg cumulative) of peanut protein with no more than mild symptoms at the Exit DBPCFC
- 2. The proportion of subjects ages 4-17 who tolerate a single highest dose of at least 300 mg (443 mg cumulative) of peanut protein with no more than mild symptoms at the Exit DBPCFC
- 3. The maximum severity of symptoms in subjects ages 4-17 occurring at any challenge dose of peanut protein during the Exit DBPCFC

4. The proportion of subjects aged 18 to 55 years who tolerate a single highest dose of at least 1000 mg (2043 mg cumulative) of peanut protein with no more than mild symptoms at the Exit DBPCFC

### **3.2.2.** Other Secondary Endpoints

The other secondary endpoints are as follows:

- Maximum dose achieved with no or mild symptoms at Exit DBPCFC in subjects ages 4-17
- Change from baseline in maximum tolerated dose (MTD) of peanut protein at DBPCFC in subjects ages 4-17
- Use of epinephrine as a rescue medication at Exit DBPCFC and comparison to its use at Screening DBPCFC in subjects ages 4-17
- Changes in peanut-specific (ps) serum IgE and IgG4 levels in subjects ages 4-17
- Changes in peanut skin prick test (SPT) mean wheal diameters in subjects ages 4-17
- Quality of life assessment using the food allergy related quality of life questionnaire (FAQLQ), and the food allergy independent measure (FAIM) questionnaire (van der Velde et al., 2010) in subjects ages 4-17

#### **3.3.** SECONDARY SAFETY ENDPOINTS

Secondary safety endpoints are as follows:

- The safety of peanut OIT based on AEs including serious adverse events (SAEs) in the following 5 age groups: 4 to 17 years, 4 to 11 years, 12 to 17 years, 18 to 55 years, and 4 to 55 years, inclusive
- Use of epinephrine as a rescue medication during OIT (Initial Escalation, Updosing, and Maintenance Periods) in the following 5 age groups: 4 to 17 years, 4 to 11 years, 12 to 17 years, 18 to 55 years, and 4 to 55 years, inclusive
- Frequency of anaphylaxis during OIT (Initial Escalation, Up-dosing, and Maintenance Periods) in the following 5 age groups: 4 to 17 years, 4 to 11 years, 12 to 17 years, 18 to 55 years, and 4 to 55 years, inclusive
- Frequency of allergic reaction (hypersensitivity) AEs during OIT (Initial Escalation, Up-dosing, and Maintenance Periods)in the following 5 age groups: 4 to 17 years, 4 to 11 years, 12 to 17 years, 18 to 55 years, and 4 to 55 years, inclusive
- Frequency of accidental ingestions of peanut and other allergenic foods in the following 5 age groups: 4 to 17 years, 4 to 11 years, 12 to 17 years, 18 to 55 years, and 4 to 55 years, inclusive

- Severity of AEs associated with accidental ingestions of peanut and other allergenic foods in the following 5 age groups: 4 to 17 years, 4 to 11 years, 12 to 17 years, 18 to 55 years, and 4 to 55 years, inclusive
- Frequency of premature discontinuation of dosing due to AEs; and frequency of premature discontinuation of dosing due to chronic/recurrent gastrointestinal (GI) AEs in the following 5 age groups: 4 to 17 years, 4 to 11 years, 12 to 17 years, 18 to 55 years, and 4 to 55 years, inclusive
- Assessment of asthma control using the Asthma Control Test questionnaire in subjects with asthma in the following 5 age groups: 4 to 17 years, 4 to 11 years, 12 to 17 years, 18 to 55 years, and 4 to 55 years, inclusive

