3.7.3 Secondary Safety Endpoints, North America and Europe

- The safety of peanut OIT based on adverse events (AEs) including serious adverse events (SAEs) in the following 5 age groups: 4 to 17 years, 4 to 11 years, 12 to 17 years, 18 to 55 years, and 4 to 55 years, inclusive
- Use of epinephrine as a rescue medication during OIT (Initial Escalation, Up-dosing, and Maintenance Periods) in the following 5 age groups: 4 to 17 years, 4 to 11 years, 12 to 17 years, 18 to 55 years, and 4 to 55 years, inclusive
- Frequency of anaphylaxis during OIT (Initial Escalation, Up-dosing, and Maintenance Periods) in in the following 5 age groups: 4 to 17 years, 4 to 11 years, 12 to 17 years, 18 to 55 years, and 4 to 55 years, inclusive
- Frequency of allergic reaction (hypersensitivity) AEs occurring during the Up-dosing versus the Maintenance Period, normalized for duration of treatment in the following 5 age groups: 4 to 17 years, 4 to 11 years, 12 to 17 years, 18 to 55 years, and 4 to 55 years, inclusive
- Frequency of accidental ingestions of peanut and other allergenic foods in the following 5 age groups: 4 to 17 years, 4 to 11 years, 12 to 17 years, 18 to 55 years, and 4 to 55 years, inclusive
- Severity of adverse events associated with accidental ingestions of peanut and other allergenic foods in the following 5 age groups: 4 to 17 years, 4 to 11 years, 12 to 17 years, 18 to 55 years, and 4 to 55 years, inclusive
- Frequency of premature discontinuation of dosing due to AEs; and frequency of premature discontinuation of dosing due to chronic/recurrent gastrointestinal (GI) AEs in the following 5 age groups: 4 to 17 years, 4 to 11 years, 12 to 17 years, 18 to 55 years, and 4 to 55 years, inclusive

• Assessment of asthma control using the Asthma Control Test questionnaire in subjects with asthma in the following 5 age groups: 4 to 17 years, 4 to 11 years, 12 to 17 years, 18 to 55 years, and 4 to 55 years, inclusive

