## **10.3. ADVERSE EVENTS**

Symptoms that are collected during in-clinic dosing visits (including DBPCFC) are not captured on the adverse event CRF page, unless the symptom is determined to be an SAE or the subject experienced an anaphylaxis episode. Thus, each of the summaries of adverse events described below will be presented in 2 different ways:

- 1. Including only events collected on the adverse event CRF page, excluding in-clinic dosing symptoms other than SAEs and anaphylaxis episodes.
- 2. Combining adverse events collected on the adverse event CRF page and dosing symptoms collected at the in-clinic dosing visits.

All reported adverse events (AEs) will be classified into System Organ Class (SOC) and Preferred Term (PT) using Medical Dictionary for Regulatory Activities (MedDRA) version 18.1.

Treatment-emergent adverse events (TEAEs) are defined as those AEs with onset after the first dose of study drug. AEs with onset prior to first dose of study drug will be included in subject listings, but not summarized. TEAEs will be summarized for the safety population by age group (4-17 years, 4-11 years, 12-17 years, 18-55 years, and 4-55 years) and by study period as follows:

- Initial Escalation: All events beginning after the first dose of study drug on Day 1 and prior to the first at-home Up-dosing administration.
- Up-dosing: All events beginning after the first dose at-home Up-dosing administration and prior to the first at-home dose of 300 mg (which starts the Maintenance Period).
- Maintenance: All events beginning after the first dose at-home dose of 300 mg, including events after the Exit DBPCFC but prior to the rollover to ARC004.
- Overall: Across initial escalation, up-dosing, and maintenance periods.

Summaries that are displayed by system organ class and preferred terms will be ordered by descending incidence of system organ class and preferred term within each system organ class. Summaries displayed by preferred term only will be ordered by descending incidence of preferred term. Summaries of the following types will be presented:

• Overall summary of number of unique TEAEs and treatment-emergent serious adverse events (TESAEs), subject incidence of TEAEs and TESAEs meeting various criteria, and exposure adjusted incidence rates of TEAEs and TESAEs

meeting various criteria, where exposure incidence rates are defined as the total number of events divided by the total number of subject-years at risk during the study period;

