- Subject incidence of TEAEs by MedDRA system organ class and preferred term;
- Exposure adjusted event rates for the most frequently-occurring TEAEs (i.e., TEAEs occurring in  $\geq$  5% of the Safety Population) by MedDRA preferred term;
- Subject incidence of TEAEs by severity grade, MedDRA system organ class, and preferred term;
- Subject incidence of TEAEs related to study drug by MedDRA system organ class, and preferred term;
- Exposure adjusted event rates for the most frequently-occurring TEAEs related to study drug (i.e., related TEAEs occurring in ≥ 5% of the Safety Population) by MedDRA preferred term;
- Subject incidence of ≥ grade 3 severity TEAEs related to study drug by MedDRA system organ class and preferred term;
- Subject incidence of SAEs by MedDRA system organ class and preferred term;
- Subject incidence of TEAEs leading to discontinuation of study drug by MedDRA system organ class and preferred term;
- Subject incidence of hypersensitivity TEAEs by MedDRA system organ class and preferred term, where hypersensitivity TEAEs are those TEAEs flagged as allergic reactions;
- Subject incidence of hypersensitivity TEAEs related to study drug by MedDRA system organ class and preferred term;
- Subject incidence of TEAEs associated with an accidental food allergen exposure by MedDRA system organ class and preferred term; and
- Subject incidence of TEAEs with onset < 90 minutes after study drug dosing by MedDRA system organ class and preferred term.

At each level of summarization (e.g., any AE, system organ class, and preferred term), subjects experiencing more than one TEAE will be counted only once within each study period. In the summary of TEAEs by severity grade, subjects will be counted once at the highest severity reported at each level of summarization.

Adverse event data will be presented in data listings by age group, treatment group, subject, study period, and event. Serious AEs; severe, life-threatening, or fatal adverse events; and AEs leading to discontinuation, reduction, or interruption of the study drug will be presented in separate data listings.

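### SAP 3.3 omits the Up-dosing versus Maintenance contrast and the duration normalization from the protocol's hypersensitivity endpoint, and SAP 10.3 does not assign its exposure-adjusted rate to hypersensitivity TEAEs

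*SAP*

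**What the plan says.** Protocol 3.7.3 lists as a secondary safety endpoint, in five age groups: "Frequency of allergic reaction (hypersensitivity) AEs occurring during the Up-dosing versus the Maintenance Period, normalized for duration of treatment". The synopsis carries the same endpoint.

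SAP 3.3 gives the corresponding endpoint as "Frequency of allergic reaction (hypersensitivity) AEs during OIT", followed by the three treatment periods and the same five age groups. The comparison between periods and the adjustment for duration are both absent.

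SAP 10.3 splits TEAE summaries by study period (Initial Escalation, Up-dosing, Maintenance, Overall) and by the five age groups. Within that structure it plans:

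- an overall summary that includes "exposure adjusted incidence rates of TEAEs and TESAEs" meeting criteria that are not listed, with the rate "defined as the total number of events divided by the total number of subject-years at risk during the study period";
- "Exposure adjusted event rates for the most frequently-occurring TEAEs", meaning preferred terms in at least 5% of the Safety Population, and the same for related TEAEs;
- "Subject incidence of hypersensitivity TEAEs by MedDRA system organ class and preferred term, where hypersensitivity TEAEs are those TEAEs flagged as allergic reactions", with a second bullet for those related to study drug.

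Only the last group names hypersensitivity TEAEs, and its measure is subject incidence. Under SAP 6.5 the denominator for incidence is a number of subjects, not person-time.

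**The concern.** The protocol asks a specific question: are allergic reactions less frequent, per unit of time, once the maintenance dose is reached? Protocol 1.2.1 reports that symptoms tended to diminish with longer treatment in earlier oral immunotherapy trials, and this endpoint would show whether that is so for AR101. The percentage of subjects with at least one event in a period does not answer it when the periods differ in length, because a longer period gives each subject more time to have a first event.

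The SAP replaces the endpoint with a broader one and does not say so. The notable changes in SAP 1.1 do not mention it, although that list covers only changes between SAP versions. SAP 12, whose title concerns changes from the protocol's analysis, lists no specific change. As written, the study report could follow the SAP in full and still not report the protocol's endpoint.

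**Working it through.** **1. The texts side by side.**

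| Element | Protocol 3.7.3 | SAP 3.3 | SAP 10.3, where hypersensitivity is named |
|---|---|---|---|
| Event | hypersensitivity AEs | hypersensitivity AEs | TEAEs flagged as allergic reactions |
| Up-dosing versus Maintenance | yes | no | by-period tables, no stated contrast |
| Adjusted for duration | yes | no | no (subject incidence) |

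**2. Whether another planned rate covers it.** The overall exposure-adjusted summary might, but its criteria are unlisted, so the text neither includes nor excludes hypersensitivity. The preferred-term rates do not replace it. Under Protocol 7.2 each symptom is recorded as its own AE with an allergic-reaction box ticked, so hypersensitivity is a flag that runs across many terms. A rate for vomiting mixes flagged and unflagged events, and flagged events under terms below 5% drop out.

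**3. Period lengths (Protocol 3.2).** Up-dosing is ideally 20 weeks and at most 40. Maintenance is ideally 24 weeks and at most 28. SAP 7.5 also assigns dosing after the Exit DBPCFC and before rollover to Maintenance, which can lengthen it further.

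**4. Effect of length on incidence.** The documents state no event rate for this endpoint, so there is no planned figure to reproduce. I assume a constant rate r per subject-year, independent events, and every subject completing the stated length.

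- Expected events per subject = r × t
- Subject incidence = 1 − exp(−r × t), with t = weeks / 52.1775

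Example, r = 1: at 20 weeks, 1 − exp(−20/52.1775) = 31.8%; at 24 weeks, 1 − exp(−24/52.1775) = 36.9%.

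With the same true rate in both periods (Up-dosing versus Maintenance, difference in percentage points):

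| r per year | 20 v 24 weeks | Difference | 40 v 24 weeks | Difference |
|---|---|---|---|---|
| 0.5 | 17.4% v 20.5% | -3.1 | 31.8% v 20.5% | +11.3 |
| 1 | 31.8% v 36.9% | -5.0 | 53.5% v 36.9% | +16.7 |
| 2 | 53.5% v 60.1% | -6.6 | 78.4% v 60.1% | +18.3 |
| 4 | 78.4% v 84.1% | -5.7 | 95.3% v 84.1% | +11.2 |

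Differences are taken before rounding. Against 28 weeks of Maintenance they run from -6.1 to -12.3 points (20 weeks of Up-dosing) and from +7.0 to +12.6 points (40 weeks).

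Raw event counts at equal rates have an Up-dosing to Maintenance ratio of 20/24 = 0.83, 20/28 = 0.71, 40/24 = 1.67 or 40/28 = 1.43. Events per subject-year give 1.00 in every case.

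**5. A true difference.** Suppose the Up-dosing rate is twice the Maintenance rate, with 20 and 24 weeks. For Up-dosing rates of 1, 2 and 4 per year, incidence is 31.8% v 20.5%, 53.5% v 36.9% and 78.4% v 60.1%. The incidence ratios are 1.55, 1.45 and 1.30, so a real twofold difference in rate is understated.

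**The case against.** The best defence is that the normalization is already in the plan. SAP 10.3 defines events per subject-year within study period, and the TEAE summaries use the same periods and age groups as the endpoint. Table layouts sit in a separate shell document (SAP 12 and 17) that may include a hypersensitivity row. The preferred-term tables would also catch much of the signal: Protocol 1.2.2.1 reports vomiting (16%) and abdominal pain (15%) as the commonest terms among hypersensitivity events in ARC001, well above 5%. Safety data are summarized descriptively (SAP 10), and no test or estimate between periods is planned, so nothing inferential is biased. Person-time would not make the periods comparable in any case, because only subjects who reach 300 mg enter Maintenance.

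Much of this stands. A reader might infer that the SAP plans nothing but unadjusted incidence; SAP 10.3 shows otherwise. A reader might also infer a much larger distortion, for example by taking a 5% weekly risk and setting a 10-week stay against 24 weeks: 1 − 0.95^10 = 40.1% against 1 − 0.95^24 = 70.8%, about 31 points. The documents give no such weekly risk, and 10 weeks is not a planned Up-dosing length; it describes early stoppers, for whom a constant risk is doubtful.

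What the defence does not supply is a commitment. The criteria for the overall rate are unlisted, the pooled flag is not the same as its commonest terms, and the only measure tied to hypersensitivity by name is the one that depends on period length. Selection into Maintenance is a caveat on interpretation, not a reason to omit an adjustment that the protocol specifies.

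**Conclusion.** The concern holds in a limited form. SAP 3.3 departs from a stated protocol endpoint without recording it, and SAP 10.3 does not say that its by-period exposure-adjusted rates include hypersensitivity-flagged TEAEs. Whether the table shells include them cannot be settled from these documents.

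For anyone comparing incidence columns across periods, the distortion is modest at the ideal lengths (about -3 to -7 points) and reverses sign if Up-dosing is prolonged (about +11 to +18 points at 40 versus 24 weeks). These sizes rest on assumed constant rates of 0.5 to 4 events per subject-year and on all subjects having the stated length; 40 weeks for everyone is an extreme.

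The efficacy analyses and the control of type I error are not affected. Nor would the adjustment alone show that reactions decline with continued treatment, since the subjects in Maintenance are a selected group.

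**What to change.** - In SAP 3.3, restore the endpoint as Protocol 3.7.3 states it: Up-dosing versus Maintenance, with the adjustment for duration.
- In SAP 10.3, add hypersensitivity TEAEs, all and related to study drug, to the exposure-adjusted event rates for Up-dosing and Maintenance, by arm and by the five age groups, using the rate already defined there. Keep the incidence tables beside them.
- Report the rates descriptively, with a note that only subjects who reach 300 mg enter Maintenance. A rate ratio between periods is optional; the protocol does not ask for one.
- If the sponsor intends the broader SAP endpoint instead, record and justify the change in SAP 12.

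The cost is one edited endpoint and about one further table from a rate that is already planned. No new data are needed.
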